2.4 POOLING OF CENTERS

Data from all sites will be pooled for analysis.

2.5 HANDLING OF MISSING DATA

Missing data will not be replaced except as noted. Missing efficacy data will be imputed in a sensitivity analysis as described in Section 7.1.6.

2.6 ANALYSIS SOFTWARE

All summaries and statistical analyses will be generated using SAS® version 9.4 or later.

3 STUDY SUBJECTS

3.1 DISPOSITION OF SUBJECTS

A data listing of Screening failures for the DB phase of the study will be provided.

Disposition will be summarized within the DB treatment groups and overall among all subjects within both the DB and OL phases of the study.

The summary of disposition will include the following:

- Subjects screened (DB phase only)
- Screen failures (DB phase only)
- Subjects in the Safety Population

- Subjects in the ITT Population
- Subjects in the PP Population
- Subjects who entered OL phase
- Subjects who completed the DB phase
- Subjects who discontinued from the study before the end of the DB phase
- Reasons for study discontinuation before the end of the DB phase
- Subjects who discontinued study drug before the end of the DB phase
- Reasons for study drug discontinuation before the end of the DB phase

Subjects completing the DB phase of the study are those who completed the 17-week DB treatment phase, regardless of whether they entered the OL. A listing of dispositions will be provided for all randomized subjects.

3.2 ELIGIBILITY CRITERIA AND PROTOCOL DEVIATIONS

The clinical team will identify protocol deviations before database lock.

A data listing of subjects who violate any of the inclusion/exclusion characteristics will be provided as well as a data listing of subjects with other protocol violations.

4 DEMOGRAPHICS AND BASELINE CHARACTERISTICS

Demographic data (age, sex race, height, weight and body mass index (BMI), and ethnicity) and baseline characteristics (Tanner staging and number of AED medications taken and stopped) collected prior to the first dose of IP will be summarized using descriptive statistics in the ITT population, the Safety population and the PP population. The statistics will be shown by DB treatment group and for all subjects combined. Tables will be provided for the ITT population overall and by biomarker stratum. Subject data listings will also be provided.

Where units differ across data points, the following conversions will be applied:

- Height (cm) = Height (inches) * 2.54
- Weight (kg) = Weight (lbs) * 0.4536
- BMI (kg/m²) = Weight (kg)/[Height(m)²]

5 MEDICAL HISTORY AND GENETIC TESTING

Medical history will be coded with the Medical Dictionary for Regulatory Activities (MedDRA) Terminology version 22.0 or higher. The number and percent of subjects reporting each diagnosis will be summarized by system organ class (SOC) and preferred

term (PT) by treatment and overall in the Safety population.

The results of the genetic testing and historical seizure information will be summarized and listed as available.

6 PRIOR AND CONCOMITANT MEDICATIONS AND THERAPIES

Prior medications/therapies are defined as medications/therapies that started and stopped prior to the first dose of DB study drug. Concomitant medications/therapies are defined as medications/therapies (other than the study drug) administered on or after the first dose of the DB study drug, regardless of when the medications/therapies started. The summary of concomitant medications/therapies for the main 17-week DB treatment phase of the study will not include concomitant medications/therapies that start after that phase; i.e., they will not include any starting on or after the first dosing day of the OL phase.

The summary of concomitant medications/therapies for the OL phase will include all medications/therapies, other than study drug, administered on or after the first dosing day of the OL phase. There will be no summary of prior medications/therapies for the OL phase.

All investigator terms for medications recorded on the CRF will be coded using the World Health Organization (WHO) Anatomical Therapeutic Chemical (ATC) drug dictionary (Version WHO Drug Dictionary, March 2014 or later). The number and percentage of subjects who took prior and concomitant medications will be summarized by treatment and overall in the Safety population and, if it differs substantially from the Safety population, the PP population as well, by ATC Classification and WHO Drug PT. Prior and Concomitant AEDs will be summarized and listed separately.

Rescue medications and associated prescribed doses reported as concomitant medications will be summarized and listed as described above. In addition, rescue medication usage data, including date and time of dosing and administered dose, which are obtained from eDiary entries, will be analyzed as exploratory endpoints as described in Section 7.1.4.6. Dose levels reported in these two sources of rescue medication data may differ.

The number (percentage) of subjects who received prior and concomitant therapies will be summarized by treatment and overall in the Safety population and, if it differs substantially from the Safety population, the PP population as well. The therapies will also be presented in a subject data listing.

To define prior or concomitant medications/therapies, Table 2 describes how missing date information will be handled; however, the actual dates, not the imputed ones, will be displayed in the listing.

Table 2: Handling of Partial or Missing Medication Dates

Partial Missing Start or Stop Date	Imputed Start Date	Imputed Stop Date
Missing year, month, and day	First dose date	
Missing month and day, and the year is present	First dose date if the year is the same as the year of first dose date, else first dose date of the OL if the year is the same as the year of the first OL dose date, else January 1 of the start year.	December 31 of that year
Missing day, but year and month are present	First dose date if the year and month are the same as the year and month of first dose date, else first dose date of the OL if the year and month are the same as the year and month of the first OL dose date, else the 1st of the start month.	Last day of that month
Missing month, but year and day are present	Assume day is also missing and impute as above	Missing month imputed as December

If an imputed start date is later than the stop date, then the stop date (after any needed imputations) will be used instead for the imputed start date.

7 EFFICACY ANALYSES

In addition to the descriptive statistics mentioned in Section 2.1, the baseline, post-baseline, and relevant changes from baseline for the seizure endpoints will also be summarized. Wilcoxon rank-sum tests will be used to compare differences in percent change from baseline between the two treatment groups.

Fisher's exact test will be used to compare the percentage of subjects achieving notable reductions, e.g. $\geq 25\%$ reduction, $\geq 50\%$ reduction, etc., in seizure rates between the two treatment groups.

The baseline, post-baseline, and changes from baseline for the other non-categorical endpoints will be summarized descriptively with 95% confidence intervals for the means and differences in means between the treatment groups.

7.1 DOUBLE-BLIND PHASE

All efficacy analyses will be conducted in the ITT population as well as by biomarker stratum. A supportive analysis of the primary efficacy endpoint also will be conducted in

the PP population.

All analyses in the ITT population will include all available data, even if they were collected after the subject stopped taking study medication, regardless of whether the subject took rescue medication. Section 7.1.1 details the handling of missing data.

For the analyses of seizures, the baseline phase consists of the 8- to 12-week period before the first day of treatment, and the DB phase starts the day following the first day of DB treatment until the final visit for subjects who do not enter the OL and up to the day before the first dose of OL treatment for those who do. Also, if a subject's baseline primary seizure count based on the prospective baseline period is less than 4, the primary seizure count from the Historical Seizure Calendar Review CRF will be used to calculate a baseline 28-day seizure count.

Tests of significance between the two treatment groups will be performed for the primary endpoint with a 2-sided significance level of 0.05.

Seizure diary compliance for the baseline and post-baseline DB phase intervals will be calculated as:

$100 \times (\text{Number of Days with Available Seizure Diary}) / (\text{Last Available Seizure Diary Date} - \text{First Available Seizure Diary Date} + 1)$.

Seizure diary compliance between visits will be calculated as:

$100 \times (\text{Number of days with available seizure data between visits}) / \text{Number of days between visits}$, with the days between visits defined as the day of the prior visit up to the day before the current visit.

Diary compliance values will be summarized with descriptive statistics and the percentage of subjects at least 80% compliant.

7.1.1 Handling of Missing Data

The primary analysis will use all available data. Careful educating and monitoring of the study sites will attempt to limit the amount of missing data. Sensitivity analyses, with replacement of missing data, will be performed for the primary efficacy endpoint; see Section 7.1.6.

For non-seizure variables, data for subjects prematurely discontinuing from the study will be assigned to the first visit subsequent to the discontinuation at which the assessment was scheduled, as long as the discontinuation visit is within 32 days of the next scheduled performance of that assessment.

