7.2.2.4. Telephone Follow-up Visit (Weeks 11, 13 ± 3 days)

A telephone follow-up visit will be conducted at Weeks 11 and 13 to assess the following:

- Adverse events
- Seizure and medication diary review

7.2.3. Final Double-Blind Visit/First Open-Label Visit, Visit 5 ± 3 days (Week 17 ± 3 days)

The following study procedures/assessments will be completed during the final DB visit or taper visit or at the time of early termination:

- Vital signs (to include BP, HR, RR, body temperature, and weight)
- Physical, neurological, and developmental examination
- ECG

- Clinical laboratory tests (to include CBC with automated differential, creatinine, blood urea nitrogen, and comprehensive metabolic panel)
- Urinalysis
- Serum pregnancy test for females of childbearing potential
- Drug screen (plasma)
- Investigational Product PK
- Concomitant AED review and levels if per SOC
- Neurosteroid level sample draw
- Adverse events
- Seizure and medication diary review
- CSHQ
- BRIEF
- ABC-C
- EEG
- PedsQL-FIM
- QI-Disability
- CGI-C (parent/caregiver/LAR identified behavioral target)
- CGI-I (parent/caregiver/LAR and clinician)
- Dispense IP (note that this will be the last dose of study medication for the DB phase and the first dose of study medication for the OL phase)

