7.4.3. Children's Sleep Habits Questionnaire (CSHQ)

The Children's Sleep Habits Questionnaire (CSHQ) is a psychological questionnaire designed to measure sleep behaviors in children and adolescents. The 33-question test is filled out by the parent/caregiver/LAR.

CSHQ will be assessed as follows: in the DB phase at Visit 2 (baseline/randomization) and Visit 5 (Week 17; also Final DB Visit/First OL Visit in OL phase); in the OL phase at Visit 7 (Week 36) and Visit 9 (Week 68) and thereafter every 16 weeks for the duration of this phase; and at the Final OL Visit.

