2.3 TIME WINDOWS FOR ANALYSIS

For by-visit safety or efficacy summaries, only scheduled visits will be analyzed.

In the analysis of seizure diary data, entries after the date of the first dose of study drug in the DB phase of the study but prior to the date of the first dose of study drug in the OL phase will be considered DB data. For subjects participating in the OL phase, entries dated after the date of first dose of study drug in the OL phase, including during the OL titration period, will be considered OL data.

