7.2 OPEN LABEL EXTENSION

All of the analyses for the DB phase will be repeated for the OL phase, with the following differences:

- All results will only be summarized descriptively.
- The results will be presented overall and classified according to the DB treatment received by the subjects
- The post-baseline seizure endpoints will be derived based on the first full day of OL treatment (one day after OL start).
- No sensitivity analyses will be performed.
- Analyses of seizure frequencies during titration and maintenance phases are only applicable to the DB phase and will not be included in the OL phase analyses.
- The time points for the efficacy, exploratory, and quality of life endpoints will be after 19 weeks, 51 weeks, and every 16 weeks thereafter of open-label treatment relative to the prospective baseline phase.
- The differences between the DB treatment groups in the percent changes from baseline of the 28-day seizure frequencies will not be tested for statistical significance.

- No PP analyses will be performed.

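### BRIEF, ABC-C and CSHQ scores taken at early termination before about Day 87 enter no double-blind summary, because of the 32-day assignment limit and the scheduled-visits rule

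*SAP*

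**What the plan says.** - **Schedule.** Protocol 7.4.3 to 7.4.5 place CSHQ, BRIEF and ABC-C "in the DB phase at Visit 2 (baseline/randomization) and Visit 5 (Week 17"), with nothing in between. Visit 5 carries a window of plus or minus 3 days (Protocol 7.2.3).
- **Collection on leaving.** Protocol 7.2.3 introduces the Visit 5 list, which includes all three scales, with: "The following study procedures/assessments will be completed during the final DB visit or taper visit or at the time of early termination".
- **Assignment rule.** For non-seizure variables, SAP 7.1.1 states that "data for subjects prematurely discontinuing from the study will be assigned to the first visit subsequent to the discontinuation" at which the assessment was due, "as long as the discontinuation visit is within 32 days of the next scheduled performance of that assessment".
- **What is tabulated.** SAP 2.3: "For by-visit safety or efficacy summaries, only scheduled visits will be analyzed". SAP 2.5 replaces no missing data unless stated, and the two imputation analyses in SAP 7.1.6 concern the primary endpoint only.
- **General statement.** SAP 7.1: "All analyses in the ITT population will include all available data, even if they were collected after the subject stopped taking study medication". The same paragraph then points to 7.1.1 for missing data.
- **Outputs.** BRIEF is summarised descriptively without a treatment comparison (SAP 7.1.3.3). ABC-C and CSHQ also get between-arm mean differences with 95% confidence intervals (SAP 7.1.3.4 and 7.1.3.5).

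**The concern.** A questionnaire completed at early termination is an observed value. If it falls more than 32 days before Week 17, however, it has no visit to belong to and so no row in any table. The SAP does not say what else should be done with it. For these three scales there is no intermediate visit to pick it up, so the subject contributes no post-baseline information to the summaries.

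The trial is small enough for this to show. About 25 subjects are expected, or 12 to 13 per arm. About 15 are expected to be biomarker-positive, or 7 to 8 per arm, and SAP 7.1.3 repeats the secondary analyses by stratum. In groups of that size one omitted score can move a mean. If those who leave the study differ in behaviour or sleep from those who stay, the ABC-C and CSHQ contrasts would not reveal it.

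**Working it through.** The plan gives no figure for this point, so there is none to reproduce. The check is day arithmetic followed by an illustration.

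**Cutoff.** Inputs: Week 17, a window of plus or minus 3 days, and the 32-day limit.

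- Nominal: 17 × 7 = Day 119; 119 − 32 = Day 87.
- Visit window: 116 − 32 = Day 84; 122 − 32 = Day 90.
- Counting the first dose as Day 1, as in the study-day formula of SAP 2.1: 120 − 32 = Day 88.
- Share of the phase before the cutoff: 87/119 = 73%. This is a share of time, not of withdrawals.

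**Example terminations.**

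| Termination at | Days before Week 17 | Assigned to Week 17? |
|---|---|---|
| Week 5 | 119 − 35 = 84 | no |
| Week 9 | 119 − 63 = 56 | no |
| Week 11 | 119 − 77 = 42 | no |
| Week 13 | 119 − 91 = 28 | yes |

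**Who is affected.** The rule concerns leaving the study. A girl who stops drug but attends Week 17 is included. Protocol 3.1 keeps such subjects in follow-up, and footnote q of the double-blind schedule encourages all procedures and visits. One who stops drug, completes the scales at a taper visit, continues the diary and then misses the Week 17 questionnaires is covered by no explicit rule.

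**Illustration.** Assumptions: N = 25, dropout of 5% to 30% (the documents state none), leaving times uniform over 119 days, and every leaver attending the termination visit. Scores left out = N × dropout × 87/119. Stayers' share of those summarised = N(1 − dropout) / (N − scores left out).

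| Assumed dropout | Leavers | Scores left out | Stayers' share under the rule | Stayers' share if all scores used |
|---|---|---|---|---|
| 5% | 1.25 | 0.9 | 99% | 95% |
| 10% | 2.5 | 1.8 | 97% | 90% |
| 20% | 5.0 | 3.7 | 94% | 80% |
| 30% | 7.5 | 5.5 | 90% | 70% |

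Stayers dominate the summaries either way. The rule removes most of the leavers who could have been included.

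**The case against.** **The window is a reasonable choice.** Under SAP 2.3 alone, no early-termination score could count as Week 17, so the 32-day rule adds data. A score from Week 2 or 3, inside the 4-week titration, does not measure a 17-week effect. This stands, and it is why the Week 17 row should stay as it is.

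**SAP 7.1 defers to 7.1.1.** A reader might infer a flat contradiction. The all-available-data sentence, though, is aimed at data after stopping drug or after rescue medication, and it is followed by a pointer to 7.1.1. What remains is a cross-reference that does not tell the reader some collected scores go unused.

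**Arm-dependent leaving is not shown.** A reader might infer it from fatigue (49.2% vs 20.4%) and somnolence (33.9% vs 5.6%), ganaxolone vs placebo, in the fragile X study described in Protocol 1.2. Those are adverse-event incidences, not withdrawal rates. The same section says that CNS-related events in the sponsor's placebo-controlled studies did not lead to stopping treatment. It does report rash leading to discontinuation in 6 ganaxolone and no placebo subjects. Neither statement gives a rate of leaving this study by arm.

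**Open label.** SAP 7.2 lists its time points ("The time points for the efficacy, exploratory, and quality of life endpoints will be after 19 weeks, 51 weeks, and every 16 weeks thereafter"), and a reader might infer that most open-label termination scores are also lost. The open-label schedule (SAP 14.1.2), however, has a column for the final open-label or taper visit, including early discontinuation, with all three scales marked. Such a score comes from a scheduled visit, which SAP 2.3 would allow to be summarised. The double-blind schedule has no such column. The text of 7.2 is silent on this visit, and the documents support no more than that.

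**The stakes are limited.** These are descriptive secondary endpoints without significance tests, and SAP 2.1 provides subject listings, so the values are not deleted. This also stands.

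**Conclusion.** For the double-blind phase the gap is real on the text. A subject who leaves the study before about Day 87 has her only post-baseline BRIEF, ABC-C and CSHQ scores left out of every summary, and out of the ABC-C and CSHQ differences, although the protocol collects them. The cutoff rests on reading 7.1.1 together with 2.3.

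The number affected is unknown. The range of about 0.9 to 5.5 of 25 rests wholly on the assumed 5% to 30% dropout and uniform leaving times. The documents do not support saying that the behavioural results describe only those who tolerated treatment, because subjects who stop drug and attend Week 17 are counted. Nor do they establish bias in a particular direction or size. The primary seizure endpoint is not touched. This is a minor point, and the change is optional.

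**What to change.** Before unblinding, amend SAP 7.1.1 as follows:

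- Keep the Week 17 row and the 32-day rule unchanged.
- For BRIEF, ABC-C and CSHQ add one supportive row, labelled last post-baseline double-blind assessment. It takes the Week 17 score or, where that is absent, the early-termination score at any time after the first dose.
- Give this row the same summaries as Week 17 and, for ABC-C and CSHQ, the same difference and 95% confidence interval.
- Report the number and timing of early scores by arm.
- In SAP 7.1, state that the all-available-data sentence is subject to 7.1.1 for non-seizure variables.

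For the open-label phase, at most add a sentence to SAP 7.2 saying that the scheduled final or early-discontinuation visit is summarised.

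The cost is SAP wording and one extra row per score, with no new data collection. The downside is that the added row mixes different lengths of treatment, including scores from titration, so it is supportive only and does not replace Week 17. Specifying it before unblinding keeps the choice independent of the results.

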The analysis of the primary efficacy endpoint will be conducted in the ITT population and within the biomarker strata of the ITT population; a supportive analysis in the PP population will also be done.

7.1.3 Secondary Efficacy Endpoints

All secondary efficacy endpoints will compare GNX and PBO during the 17-week DB treatment phase relative to the prospective baseline phase, unless specifically indicated otherwise.

All secondary analyses will be done in the ITT population for all subjects and by biomarker stratum, and if the ITT and PP analyses notably differ for the primary endpoint, they will also be done in the PP population. All seizure control endpoints will be included in data listings.

7.1.3.1 Percent Change in Primary Seizure Frequency in Biomarker Positive Stratum

If the results of the primary endpoint analysis in the full ITT population indicate efficacy in the GNX treatment arm, the primary efficacy analysis described in Section 7.1.2 will be repeated for subjects in the biomarker-positive stratum.

7.1.3.2 Percentage of Subjects Experiencing Primary Seizure Reduction

Percentages of subjects experiencing a $\geq 50\%$ reduction in 28-day primary seizure frequency relative to baseline will be compared between GNX and PBO for both biomarker-positive and negative strata, separately, and for the combined strata. A Fisher's Exact test will be used to compare rates between treatment groups.

7.1.3.3 Behavior Rating Inventory of Executive Function (BRIEF, preschool version BRIEF-P)

The BRIEF is an 86-item questionnaire designed to assess executive function behaviors in the school and home environments in individuals 5-18 years of age. The preschool version (BRIEF-P) is a 63-item modified form and will be administered to individuals 2-5 years of age. The BRIEF version to be administered will be based on the subject's age at Screening. The same version of the BRIEF will be administered during the entire study regardless of the subject's age at the time of post-screening assessment. The questionnaire is completed by the parents/caregiver/ legally authorized representative (LAR).

The BRIEF items are partitioned to create 8 component scores:

- Inhibit
- Shift
- Emotional Control
- Initiate
- Working Memory
- Plan/Organize
- Organization of Materials
- Monitor

The first three components are summed to create a Behavioral Regulation Index (BRI), and the remaining five components are summed to create a Metacognition Index (MI). The BRI and MI are then summed to create a Global Executive Composite (GEC).

The BRIEF-P items are partitioned to create 5 component scores:

- Inhibit
- Shift
- Emotional Control
- Working Memory
- Plan/Organize Scales

The Inhibit and Emotional Control components are summed to create an Inhibitory Self-Control Index (ISCI), the Shift and Emotional Control components are summed to create a Flexibility Index (FI), the Working Memory and Plan/Organize components are summed to create an Emergent Metacognition Index (EMI), and all five components are summed to create a Global Executive Composite (GEC).

All component scores, index scores, and composite scores will be descriptively summarized. Both baseline, post-baseline, and change from baseline will be summarized. These scores will also be listed. Statistical comparison between treatment groups will not be performed.

